7.1.2.6 Lumbar Puncture

Subjects will have the option of participating in three lumbar punctures over the course of the study (at Days 28, 84 and 140). Lumbar punctures will be performed after a minimum of an 8 hour fast. The subject will be positioned seated or lying on his/her side on the examination table. Standard protocols will be used employing palpation to identify the L3-4, L4-5 or L5-S1 vertebral interspaces, sterile conditions, local lidocaine anesthesia, and use of the Sprotte 24-gauge needles. Lumbar punctures will be performed by qualified, experienced practitioners. Approximately 20 cc of CSF will be collected for analysis of various AD/ADRD, redox, and metabolism and other biomarkers, including NfL, 8-OHdG, pyruvate/lactate, tau, phospho-tau, amyloid-β42/40, and neurogranin. Subjects will also complete a brief REDCap survey after the LP in which they will answer questions about the tolerability of the procedure. After the LP is complete, subjects will be given time to eat breakfast or have a snack before continuing with the visit.

If a subject has difficult back anatomy or is particularly overweight, and the physician or nurse practitioner does not feel comfortable performing the LP because they are not able to locate the proper lumbar landmarks, the subject will be scheduled to undergo the LP under fluoroscopy at MGH Interventional Radiology. Fluoroscopy time will vary person to person. The average radiation dose is 0.06 mSv, or the equivalent of 1 week of natural background radiation, per LP for a total of 0.2 mSv (3 weeks of natural background radiation) over the duration of the study.

7.1.3 Daily Outcomes

A Crossover, Randomized Block Sequence, Double-Blind, Placebo-Controlled Trial for Nicotinamide Riboside in Subjective Cognitive Decline and Mild Cognitive Impairment in Aging

Version:4.4

7.1.3.1 Mood and sleep ratings

Before beginning each Lumosity session, the subject will be asked to rate their mood and sleep. The survey will consist of two brief questions and require no more than two minutes of the subject's time.

7.1.3.2 Cognitive Exercises

Each subject will be provided with a Lumosity (Lumos, Labs, Inc.) account. The subjects will be required to complete 6 different cognitive exercises (about 10-15 minutes) at least 6 days per week for the duration of the study (from Days 0 to 140). The assigned cognitive exercises will sample the domains of attention, processing speed, memory, cognitive flexibility, and problem solving. Compliance can be assessed by the study coordinator by logging on to each subject's Lumosity account. If the subject is not adhering to the cognitive exercise requirements, the study coordinator will contact the subject to remind them of proper exercise procedures. If a subject requires more than three such reminders, they will be considered non-compliant, and PI will determine if the subject should continue in the study or if their study participation should be discontinued.

7.1.3.3 Daily activity and sleep tracking

Each subject will be provided with a Fitbit Charge 4 that they will wear throughout the study. The device will track the participant's heart rate, activity, and sleep. The subject will be instructed to wear their device at all times, except for when it is being charged and when they are bathing.

7.1.3.3.1 Charging and syncing procedures

Subjects will be instructed to ensure that the device is charged at all times. The subject will be instructed to charge their device when their battery is low (roughly once every 4 days) during a period of inactivity, such as when watching TV. The subject will be explicitly instructed not to charge their device during times of sleep. The subject will be instructed to sync their device at least 3 times per week. Charging and syncing compliance will be routinely monitored by a study coordinator. The coordinator will conduct periodic reviews of the subject's charging and syncing compliance by logging onto the subject's Fitbit dashboard. If the device has not been appropriately charged or synced, the study coordinator will contact the subject to remind them to sync or charge their device as needed. If a subject requires more than three such reminders, they will be considered non-compliant, and the PI will determine if the subject should continue in the study or if their study participation should be discontinued.

7.2 Training and Validation

All evaluators must be certified by the study PI to perform cognitive and psychiatric outcome assessments. It is strongly preferred that a single evaluator performs all measures with a given instrument throughout the study, if possible.

8. INTERVENTIONS ADMINISTERED

8.1 INTERVENTION

8.1.1 Study Product Description

Niagen® is a commercially available form of nicotinamide riboside (NR) manufactured by ChromaDex, Inc. Niagen® is generally recognized as safe (FDA GRAS Notice No. 635) for use in a variety of media, including vitamin waters, protein shakes, and powdered beverages. Niagen® has five issued process and use patents in the United States and several others internationally.

Chemical Structure of nicotinamide riboside:

8.1.2 Drug and Placebo

Chromadex Inc. will provide 250 mg capsules. Identical appearing capsules with only filler will be prepared as placebo.

8.1.3 Acquisition

When the study intervention shipment arrives at the site, the person accepting the shipment must perform an inventory and fill out a supplement receipt log. The contents of the shipment must be counted, verified, and inspected for damage. Any damaged shipments will be documented. The study supplement will be picked up from MGH Clinical Trials Pharmacy on the same day it will be dispensed. Detailed logs will be kept recording quantity of supplement dispensed and study staff in charge of supplement transport and dispensing.

8.2. Product Storage and Stability

Niagen NR is found to be stable under ambient conditions of 25 °C and 60% relative humidity for 11 months in a solid, powdered form.

8.3 Dosage, Preparation and Administration of Study Intervention

Niagen NR 500 mg (two capsules) or PBO (two capsules) should be taken orally twice daily with food. The capsules should be swallowed whole.

A Crossover, Randomized Block Sequence, Double-Blind, Placebo-Controlled Trial for Nicotinamide Riboside in Subjective Cognitive Decline and Mild Cognitive Impairment in Aging

Version:4.4

8.4 Modification of Study Intervention for a Subject

Dosing may be reduced or suspended at any time by the PI or designated licensed clinician sub-investigator. This will be documented along with the reason(s) and dates of adjustment in the CRF for each subject requiring this manipulation. The PI or designated licensed clinician Sub-Investigator may reduce or suspend the dosage of study dietary supplement or discontinue the study supplement for AEs thought to be related to the study supplement or for other reasons during the trial (the reason and dates of reduction or suspension or dose reduction or suspension must be documented in CRF). If the AE is mild or moderate, the dosage may be restarted after the event improves. If the AE is serious or life threatening and deemed to be definitely related to the dietary supplement, the study dietary supplement will be discontinued immediately. Study subjects must remain off the study dietary supplement permanently. Subjects may not resume study dietary supplement. All AEs will be followed to resolution.

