5.4 Reasons for Withdrawal

A study subject will be discontinued from participation in the study if:

- Any clinical adverse event (AE), concurrent illness, or other medical condition or situation occurs such that continued participation in the study would not be in the best interest of the subject.
- The subject meets any exclusion criteria (either newly developed or not previously recognized).
- The subject is less than 80% or greater than 120% compliant with NR dosing.

Subjects are free to withdraw from participation in the study at any time upon request.

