8.4.1 Dosage Discontinuation

Reasons for discontinuation of study dietary supplement may include an AE or PI recommendation, protocol deviation, loss-to-follow-up, patient request, or death. All serious adverse events (SAEs) that occur in a subject who has discontinued early must be recorded and reported within 24-hours of awareness. Study subjects who discontinue study dietary supplement prematurely (early discontinuation from study) and decide not to remain in the study will be encouraged to return for an Early Termination Visit.

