Subjects will be monitored for AEs from the time they sign consent until completion of their participation in the study (defined as death, consent withdrawal, loss to follow up, early study termination for other reasons, or following completion of the entire study). An unexpected adverse event is any adverse event, the specificity or severity of which is not consistent with the current Investigator's Brochure.

The study procedures and the well-being of all participants will be monitored closely by the MGH principal investigator, [name] MD, and the Co-Investigators, [name] and [name] DNP, FNP-BC. Throughout the course of the study, constant feedback with the subject is maintained in order to assess comfort and safety and to minimize risks throughout the procedure. The above investigators will be responsible for determining if a subject should be removed from the study. Criteria for removal include the following: 1) if a subject is unwilling or unable to participate in study procedures 2) if the subject refuses to participate and consent, 3) if the subject acquires a medical condition that prohibits further participation, 4) if in the opinion of the MGH principal investigator, [name], it is decided that it is not in the subject's best interest to continue participation.

Unanticipated problems including adverse events will be reported to the Partners Human Research Committee (PHRC) as described in the PHRC policy on Unanticipated Problems Involving Risks to Subjects or Others including adverse events.

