11.4.2 Relatedness of Adverse Event to Investigational Protocol

1. Not Related:	Concomitant illness, accident, or event with no reasonable association with protocol.		
2. Unlikely:	The reaction has little or no temporal sequence from administration of the investigational		
	protocol, and/or a more likely alternative etiology exists.		
3. Possibly Related:	The reaction follows a reasonably temporal sequence from administration of the		
	investigational protocol and follows a known response pattern to the suspected		
	investigational protocol; the reaction could have been produced by the investigational		
	protocol or could have been produced by the subject's clinical state or by other modes of		
	therapy administered to the subject.		
4. Probably Related:	The reaction follows a reasonably temporal sequence from administration of investigational		
	protocol; is confirmed by discontinuation of the investigational protocol or by re-challenge;		
	and cannot be reasonably explained by the known characteristics of the subject's clinical		
	state.		
5. Definitely Related:	The reaction follows a reasonable temporal sequence from administration of investigational		
	protocol; that follows a known or expected response pattern to the investigational protocol;		
	and that is confirmed by improvement on stopping of the investigational protocol, and		
	reappearance of the reaction on repeated exposure.		

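### If *definitely related* in section 8.4 carries its only protocol definition (11.4.2), the mandatory permanent stop cannot be triggered when a reaction first occurs

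*Combined protocol and SAP*

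**What the plan says.** Section 8.4 sets three levels of action on study product.

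- **Discretionary.** The principal investigator (PI) or a designated clinician may reduce, suspend or discontinue product for AEs thought to be related, or for other reasons.
- **Restart.** "If the AE is mild or moderate, the dosage may be restarted after the event improves".
- **Mandatory.** The trigger and action read: "serious or life threatening and deemed to be definitely related to the dietary supplement, the study dietary supplement will be discontinued immediately". The subject then stays off product for good: "Subjects may not resume study dietary supplement".

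Section 11.4.2 holds the protocol's only relatedness scale, with five grades. The top grade, *definitely related*, requires a reasonable time sequence and a known or expected response pattern. It also requires that the reaction "is confirmed by improvement on stopping of the investigational protocol", and "reappearance of the reaction on repeated exposure". These conditions are joined by *and*.

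Other provisions can also take a subject off product. Section 5.4 discontinues a subject when an AE means that "continued participation in the study would not be in the best interest of the subject". Section 11.3.1 lists, among its removal criteria, the PI's opinion that it is not in the subject's "best interest to continue participation". Section 8.4.1 adds: "Reasons for discontinuation of study dietary supplement may include an AE or PI recommendation".

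**The concern.** A rule that says to stop at once, and never restart, is meant for the moment a serious reaction appears. If its trigger is a grade that can be awarded only after a stop and a re-exposure, it is not available at that moment. The one stop tied explicitly to seriousness and relatedness would then give way to case-by-case judgement, and whether product could later be resumed would be unclear. What is at stake is subject safety and consistent handling of product under the blind. The primary RBANS comparison is affected only through any subjects who are stopped.

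**Working it through.** No figure in the plan needs reproducing, so the check sets the texts side by side.

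**Step 1: which 11.4.2 grades can be awarded, and when.**

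| Point in time | Dechallenge known? | Rechallenge known? | Highest grade | 8.4 mandatory stop triggered? |
|---|---|---|---|---|
| Reaction first occurs, product not yet stopped | no | no | possibly related | no |
| Product stopped, reaction improves | yes | no | probably related | no |
| Product restarted, reaction returns | yes | yes | definitely related | yes, if serious or life threatening |

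*Probably related* needs confirmation by stopping or by re-challenge. *Definitely related* needs both. At first occurrence, 0 of the 2 confirmations are available. On this definition the rule needs at least two exposures separated by a stop.

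**Step 2: where a re-exposure could come from.** Under section 3.1 each sequence contains a single 8-week NR block, so the schedule itself gives no second exposure to NR. Re-exposure would have to come from a restart of blinded product. One route exists. A mild or moderate episode resolves off product, product is restarted as 8.4 allows, and the reaction returns as serious. The definition can then be met at the first *serious* episode. The accurate limit is therefore the first occurrence of the *reaction*.

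**Step 3: does the bar on resumption reach the other stops?** The bar directly follows the *definitely related* sentence. Nothing in 8.4 or 8.4.1 extends it to a discretionary stop. A stop under 5.4 ends participation and no re-entry is described, so the question matters mainly for product stopped under 8.4 or 8.4.1.

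**Step 4: severity against seriousness.** Section 11.4.1 records severity (mild, moderate, severe) and seriousness as separate items. Section 11.3.2 makes an AE serious if, for example, it requires inpatient hospitalization. A hospitalised AE of moderate severity is therefore serious and also moderate. Unless it is graded *definitely related*, the mandatory stop does not apply, and the restart sentence literally does.

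**Step 5: size.** The documents give no rate of serious related reactions. Section 2.1.5 describes a crossover trial in 30 healthy subjects with 14 AEs in 7 subjects, all mild. A zero-event limit can be computed from it: 1 − 0.05^(1/30) = 9.5% (one-sided 95%). That bounds AEs above mild severity, not serious related ones. It also assumes all 30 took NR, although two dropped out during placebo. It is illustrative only and carries no weight here.

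**The case against.** The strongest reply is that the defect depends on a link the text does not make. Section 8.4 does not cite 11.4.2. It speaks of relation to the dietary supplement, while 11.4.2 grades relation to the investigational protocol, and the word *deemed* points to clinical judgement. An investigator could read *definitely related* in its ordinary sense and stop product at once. This stands, and it makes the point conditional. It does not dispose of it. The phrase is the exact name of a defined grade, every reported AE is assessed for its relation to the investigational protocol, and no other definition is offered. A stop rule should not depend on which reading an investigator picks.

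The second reply is that stopping is already covered. This also largely stands. Section 5.4 is mandatory once its best-interest condition is met and has no relatedness or rechallenge threshold, and the PI may suspend dosing at any time. A reader might infer that the protocol leaves no way to stop product after a first serious reaction, or that it calls for rechallenge. The documents support neither: nothing requires continued dosing, and the only express restart permission is for mild or moderate AEs.

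The third reply is that choosing a lower relatedness threshold is partly preference. That stands too. *Possibly related* includes events that the subject's clinical state could have produced. Of the 4 + 8 + 8 = 20 weeks on capsules, 4 + 8 = 12 are placebo. If background serious events fell evenly over time, 12/20 = 60% would occur on placebo.

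**Conclusion.** The point holds in conditional form. If *definitely related* in 8.4 carries the 11.4.2 definition, the mandatory immediate and permanent stop cannot be met at the first occurrence of a reaction. Stopping then rests on the best-interest rules in 5.4 and 11.3.1 and on PI discretion, and 8.4's bar on resumption does not clearly attach to those stops. The severity and seriousness mismatch does not depend on that condition: as worded, a serious AE of moderate severity can come under the restart sentence.

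A reader might go further and conclude that the rule can never act. That is too strong, given the ordinary-sense reading and the restart route in Step 2. Practical harm is limited because other provisions can stop product. Few subjects are likely to be affected, which is a judgement from the mild AEs in section 2.1.5, since no rate of serious related reactions is given. The wording is still worth correcting, because the remedy is cheap and concerns safety.

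**What to change.** Change two sentences in section 8.4.

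1. For a serious or life-threatening AE that the investigator judges, at the time, to be related to study product, stop immediately and permanently with no resumption. State that this judgement needs no dechallenge or rechallenge.
2. State that restart applies only to non-serious AEs of mild or moderate severity.

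The relatedness threshold is for the sponsor to choose. A reasonable possibility, or *possibly related* or higher, is one option. If the 11.4.2 grade is used, note that *possibly related* as defined also asks for a known response pattern, so a novel reaction could miss it.

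No new procedures are needed. The downside is possibly a few more permanent stops, some on placebo, with some loss of paired data. A stop in the lead-in loses both on-product conditions. A stop in the first block cuts that condition short and loses the second, and a stop in the second block cuts the second short. Purely as illustration, with the standard error of the paired comparison proportional to 1/√n, losing 1 of 40 subjects raises it by √(40/39) − 1 = 1.3%, and losing 4 raises it by √(40/36) − 1 = 5.4%. These counts are assumptions, not forecasts, and some of these subjects might be stopped under 5.4 anyway.

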8.4.1 Dosage Discontinuation

Reasons for discontinuation of study dietary supplement may include an AE or PI recommendation, protocol deviation, loss-to-follow-up, patient request, or death. All serious adverse events (SAEs) that occur in a subject who has discontinued early must be recorded and reported within 24-hours of awareness. Study subjects who discontinue study dietary supplement prematurely (early discontinuation from study) and decide not to remain in the study will be encouraged to return for an Early Termination Visit.

8.5 Assessment of Subject Compliance

Subjects will be instructed to return empty and unused study dietary supplement containers at each clinic visit or the Early Discontinuation Visit. Research staff will review returned and unused study dietary supplement and log information into the reconciliation form to determine compliance. Non-compliance will be defined as taking less than 80% or more than 120% of study agent as determined by unused capsule counts. If a study subject is non-compliant with study dietary supplement, research staff should re-educate and train the subject in administration of study agent. If the subject's non-compliance persists, it will be left up to the PI to determine whether the subject should be discontinued from the study.

9. STATISTICAL ANALYSIS

9.1 Biostatistical analysis

This is a crossover randomized controlled trial with the goal of determining the effects of a potential cognitionenhancing dietary supplement for older adults with SCD and MCI. The primary analysis will be based on an intention to treat approach and will include all subjects randomized at the onset of the trial to either NR then placebo or placebo then NR as described below.

In this study, the participants will pass through intervention blocks with administration of both NR and PBO for eight weeks administered in random order. The primary cognitive outcome measure will be the Total Scale score of the RBANS which will be administered at Baseline (Day 28), Crossover (Day 84), and End of Study (Day 140). The RBANS is a robust 25-minute, standardized neurocognitive battery with multiple alternate versions whose 12 subtests yield five Index scores, one for each cognitive domain, and the Total Scale score.

A Crossover, Randomized Block Sequence, Double-Blind, Placebo-Controlled Trial for Nicotinamide Riboside in Subjective Cognitive Decline and Mild Cognitive Impairment in Aging

Version:4.4

Normative data have been published for cognitively normal older adults, as well as for MCI and AD populations. For example, in a study of MCI, the mean Total Score Index was reported to be 92.4 with a standard deviation of 9.1⁴³. Based on test-retest reliability, a minimal detectable change in community-dwelling older adults (including normal, MCI and mild dementia) for the Total Score is 5⁴³. A "minimum clinically important difference" in MCI was reported to be 8 points⁴⁴.

The basic data of a crossover trial are the measurements obtained in 2 or more different intervention conditions occurring over time. The principal goal is to compare outcomes for each condition within a randomized block structure while accommodating repetition *within* subjects and possible effects of carryover or disease progression.

Assessment of normality of data distribution will be completed prior to inclusion in any analysis. If the distribution of the outcome variables (e.g., RBANS Total Score, etc) are not normal, appropriate transformations (e.g., logarithm, square-root, Box-Cox transformation, etc) will be applied. Data analysis at the individual and group levels for the primary outcome will begin with visual inspection of RBANS Total Scores at each assessment for differences from baseline for each measurement and differences between intervention conditions. Ignoring potential for carryover, a simple matched pair t-test will be performed using data from each condition. Should carryover effects or other time trends be suspected, we can use a regression model adjusting for sequence.

Mixed-effects models will be used to compare the scores at the end of each study period (Days 28, 84, and 140) between NR and PBO incorporating variance within and between participants. This within-patient level will accommodate variation resulting from the intervention crossovers as well as time effects modeled in various forms (e.g., linear and non-linear trends, carryover effects). Each within-subject regression coefficient will be treated as a random effect that can vary based on these between participant factors. The primary analysis will calculate the average intervention effect (i.e., will model the mean of the individual intervention effects as a constant). Secondary analyses will model the mean as a function of factors that vary among patients such as age and sex. These terms describe the main effects of these factors, their interactions with the intervention, and their interaction with time. The analysis will be completed using SAS PROC MIXED through a restricted maximum likelihood analysis with a mixed model with fixed effects for sequence and treatment. Appropriate covariance structure will be investigated using Akaike's information criterion (AIC).

The full multilevel model will estimate both average effects across the population of participants, as well as effects for individuals informed by the results on other participants. The predicted effects for an individual participant are weighted averages of his or her data and the averages from others. This model incorporates correlations among the measurements within an individual and enables comparison of the individual's predicted intervention effect using the multilevel model with that from using only that individual's data.

When conducting study analyses we can also calculate 95% confidence intervals for the difference in response for active treatment versus placebo treatment for descriptive purposes. Similar analyses will be applied to all

A Crossover, Randomized Block Sequence, Double-Blind, Placebo-Controlled Trial for Nicotinamide Riboside in Subjective Cognitive Decline and Mild Cognitive Impairment in Aging

Version:4.4

outcomes. All outcomes in this pilot study are considered exploratory and no claims are attached to them, thus multiple comparison correction is not applied. Therefore P value <0.05 will be considered significant.

Carryover is always a potential confound in crossover studies. While the pharmacokinetic half-life of NR is short (2.7 hours), its pharmacodynamic effects may be long-lived and we cannot exclude carryover and practice effects affecting measures in successive assessments if NR precedes PBO. We do not expect carryover pharmacological effects from PBO, but assessment practice effects might differentially affect measurements made in an NR intervention period that follows PBO. This may be difficult to gauge with our primary RBANS outcome measure taken only once at the beginning/end of each intervention period. However, we will have other resources with which to evaluate this using our exploratory outcomes, especially the daily cognition measures. We will investigate various adjustments for carryover, such as discarding the first measurements in an intervention period on outcomes measured daily, to determine whether results are sensitive to carryover. These adjustments can allow for potential differential carryover by intervention regimen.

